6.5 GENERAL CLINICAL ASSESSMENTS

- Electrocardiogram (EKG).
- Echocardiogram.

6.6 DISEASE-SPECIFIC ASSESSMENTS

- Pulmonary function testing. Spirometry (FVC and FEV1) with DLCO. DLCO will be
 calculated according to the Global Lung Function Initiative (GLI) all-age reference
 values and corrected for hemoglobin [82, 83].
- Modified Rodnan Skin Score (mRSS).
- Physician global assessment.
- Patient reported outcomes (patient global assessments, PROMIS-29, SHAQ-DI) [84].

6.7 MECHANISTIC ASSESSMENTS

- Punch skin biopsies will be collected from fibrotic-skin areas.
- Plasma/Serum assays.
- PBMC assays.
- Whole blood DNA genotyping.
- Whole blood gene expression analysis.

7. MECHANISTIC ASSAYS

7.1 MECHANISTIC HYPOTHESES AND RATIONALE

SSc is characterized by fibrosis, inflammation, and micro vasculopathy in multiple organ systems, and there is substantial evidence linking these symptoms to an underlying autoimmune pathogenesis [14]. Nearly all patients diagnosed with SSc have anti-nuclear antibodies as well as other clinically–associated autoantibodies present in circulation [15]. Furthermore, biopsies taken from skin of SSc patients show infiltration of activated T cells [17], and this infiltration correlates with skin thickening, suggesting a relationship between fibrosis in the skin and inflammation. Recent data also suggests a key role for Th2 cells in skin fibrosis in which production of pro-fibrotic cytokines by Th2 cells ultimately leads to altered gene expression in skin fibroblasts [24].

CD30 is expressed on several immune cell subsets, but reports suggest that the subpopulation of Th2 cells implicated in SSc skin fibrosis may preferentially express CD30 [25, 31]. Therefore, the primary mechanistic hypothesis is that brentuximab vedotin will alter the balance of pro- versus anti-fibrotic effects of autoreactive T cells by impacting pathogenic Th2 cell populations expressing CD30 in the skin and/or peripheral blood. Brentuximab vedotin may also alter functional properties of new and/or pre-existing T cell subtypes not eliminated by treatment in skin or blood. Given that CD30 is also expressed by activated B cells and natural killer (NK) cells [27, 85] it is possible brentuximab vedotin will alter the frequency and/or functional properties of these immune cell types in skin and/or blood as well. Mechanistic studies will address multiple questions but will be prioritized based on the amount of tissue and blood available.

In this study, skin and blood samples will be collected with the objective of analyzing cellular infiltration and circulating immune cell populations, cytokine levels both in skin and circulation, autoantibodies, soluble CD30, and genetic signatures of disease, inflammation, and fibrosis. It is hypothesized that treatment with brentuximab vedotin may result in: 1) impact on CD30 expressing cells resulting in alterations in the number, proportion, and/or functional status of effector and regulatory T cells in peripheral blood and affected skin [25, 86-92], 2) favorable changes in gene expression in affected skin, specifically, downregulation of inflammatory and pro-fibrotic gene signatures and the expression of specific genes that have clinically-predictive value [93-96]. The following hypotheses will also be explored: 1) changes in the presence and titer of antinuclear

antibodies and other SSc-associated autoantibodies, 2) changes in the levels of circulating soluble CD30.

7.2 PLANNED MECHANISTIC ASSAYS

Two skin biopsies will be collected from fibrotic-skin areas at weeks 0, 12, and 24. One biopsy will be used for RNA isolation and one biopsy for immunohistochemical analysis. Blood will be collected at week 0, 12, 24 and 48 in ABI TempusTM blood collection tubes for gene expression analysis, in serum clot tubes for serum assessments, and in heparinized tubes for PBMC isolation and plasma characterization.

7.2.1 Local Immune Responses in the Skin

7.2.1.1 Immunohistochemistry/In Situ Hybridization (IHC/ISH)

One of the two skin biopsies will be preserved for IHC/ISH upon collection. Skin sections may be stained with antibodies directed against T-cells and cytokines. Cellular infiltration can be compared between treatment groups to evaluate the efficacy of treatment on reducing the Th2 subsets and associated inflammatory and pro-fibrotic cytokines.

7.2.1.2 Gene expression of RNAlater® biopsies

CD30+ Th2 cells are critical to the pathogenesis of SSc and can be detected in lesional skin and blood [27, 34]. Treatment with brentuximab vedotin may impact CD30+ Th2 cells in affected skin resulting in reduced lesional levels of pro-fibrotic Th2 cytokines such as IL-4, and stabilization or reduction in molecular signatures of active fibrosis in SSc lesions.

Skin biopsies will be collected from enrolled participants to evaluate transcriptional changes following treatment with brentuximab vedotin. One of the two skin biopsies will be submerged in RNAlater® upon collection for evaluation of gene expression profiles. RNA will be isolated, and gene expression of selected cytokines and other immune regulatory molecules will be further evaluated using methods such as microarray, Nano string or RNA-seq.

Biopsy tissue will be compared pre- and post-treatment to determine the effect of treatment on the global gene expression in participants with SSc. Care will be taken in the interpretation of data comparing participants since the drug effects of immunosuppressive therapy for SSc at the time of enrollment may confound mechanistic observations. Therefore, comparisons at baseline will be performed to evaluate inflammatory signatures in the participants prior to treatment with brentuximab vedotin.

7.2.2 Cellular Assays

7.2.2.1 Peripheral Blood Mononuclear Cell (PBMC) preparation

All blood samples collected for PBMC isolation will be shipped from the clinical sites to the ITN core facility for processing using ITN standard operating procedures (SOPs) for PBMC separation and freezing. This will ensure that standardized procedures are used,

Protocol ITN075AI: BRAVOS Brentuximab Vedotin for Systemic Sclerosis and that high quality material is obtained for testing. PBMCs will be stored in the vapor phase of liquid nitrogen until use.

7.2.2.2 Multi-parameter immunoprofiling of PBMC

Flow cytometry or mass cytometry may be done at ITN laboratories to analyze the impact of treatment on the frequency and functional status of specific immune cell populations in viably cryopreserved PBMC. We will investigate the hypothesis that treatment with brentuximab vedotin will impact CD30-expressing cells in peripheral blood. This may alter the proportion of activated effector T cell subtypes in the CD4 and CD8 T cell compartments, the ratio of effector T cell subsets to regulatory T cells, and/or the proportion of activated B cells and NK cells in the peripheral blood.

7.2.2.3 Quantification of autoreactive B cells

Activated B cells may express CD30 on their surface, thus treatment with brentuximab vedotin may have an impact on circulating B cells, specifically autoreactive B cells. Enzyme-linked immunospot (ELISPOT) assays may be used to quantify B cells with reactivity towards nuclear antigens. The kinetics of this response may be measured, and comparisons could be made between baseline and the time points following treatment.

7.2.2.4 Epigenetic analysis of PBMC

Recent data has emphasized the importance of epigenetic modifications in the pathogenesis of many disorders, including SSc [97, 98]. Current evidence demonstrates alterations in DNA methylation and histone code modifications in cells from patients with SSc [99]. While studies have revealed the significant role of epigenetic modifications in the pathogenesis of SSc, the causal nature of epigenetic alterations in SSc pathogenesis, as well as the effects of specific treatments, remains elusive. Epigenetic studies may therefore be designed to investigate correlations with disease progression and therapeutic response.

7.2.3 Serum and Plasma Assays

7.2.3.1 Serum cytokine assays

Alterations in presence or function of effector T cell populations due to treatment with brentuximab vedotin may result in changes in the gene expression profile in SSc patients [93-96]. Participant serum/plasma may be analyzed to investigate the impact of treatment on circulating levels of cytokines and inflammatory mediators. Longitudinal assessment of serum cytokines and inflammatory mediators may be performed using immunoassay platforms. Additionally, the impact of treatment on levels of cytokines and inflammatory mediators could be evaluated for correlations with changes in immune cell populations and/or gene expression in peripheral blood and skin.

7.2.3.2 Autoantibody titers

SSc is associated with several autoantibodies that may be clinically relevant in determining the diagnosis and prognosis of affected individuals [100]. Given that activated B cells may express CD30, treatment with brentuximab vedotin may impact

Version 5.0

Protocol ITN075AI: BRAVOS Brentuximab Vedotin for Systemic Sclerosis autoantibody production [27, 85]. To explore the impact of treatment on autoantibody titers, participant serum may be analyzed for circulating levels of antinuclear or other autoantibodies by ELISA or similar method. Longitudinal assessment of autoantibody levels could be compared between baseline and the time points following treatment.

7.2.3.3 Soluble CD30 levels

Circulating levels of soluble CD30 in patients with SSc have been shown to correlate with disease activity of SSc [32, 33]. Elimination of CD30+ cells may lower sCD30, which could be a biomarker of response to brentuximab vedotin. In order to explore the impact of treatment on soluble CD30, participant serum may be analyzed for circulating levels of soluble CD30. Circulating levels of soluble CD30 could be compared between baseline and the time points following treatment.

7.2.4 Whole Blood Assays

7.2.4.1 Whole blood DNA genotyping

It is reasonable to assume that treatment may not be equally effective in all individuals and that genetic differences may, in part, determine response. DNA may be isolated from whole blood collected from all consenting participants, and the ITN may perform genotyping for HLA Class I/II alleles or single nucleotide polymorphisms (SNPs) in selected immune response genes to investigate correlations with disease progression and therapeutic response.

7.2.4.2 Gene expression in peripheral blood.

Systemic treatment with biologic medications has been shown to modulate gene expression in autoimmune disease; therefore, whole blood can be used to evaluate changes in the peripheral circulation due to immunomodulation of the disease or the systemic nature of the treatment. Whole blood will be collected from enrolled participants and may be used to evaluate global changes in gene expression during and after treatment. Gene expression of selected cytokines and other immune regulatory molecules may be further investigated using quantitative methods.

7.3 RETENTION OF SAMPLES

A major priority of the Immune Tolerance Network, in partnership with the National Institute of Allergy and Infectious Diseases of the NIH, USA, is the development of novel immunoassays in order to better understand mechanisms of tolerance and to develop biomarkers to predict the development and maintenance of clinical tolerance. As in all Immune Tolerance Network-funded clinical trials, informed consent will be obtained from all participants for their samples to be stored for use in future studies. Biological specimens collected in this trial will be stored long-term in order to reevaluate biologic responses as new research tools to study tolerance become available. The specimens will therefore be stored at the ITN sample repository for a minimum of 10 years. Residual specimens may be used by the investigators for development of new immunologic assays or for cross-trial comparisons. Although specimens in this protocol

are described in the context of assays to be performed, it should be noted that not necessarily all assays will be performed for all participants at each time point. Decisions to perform assays will be made based on statistical and scientific planning, hypotheses to be tested, and technologies available. Finally, clinical outcomes will be taken into account to determine the potential value of the assays. For example, if a clinical effect fails to occur, it may be decided that there is minimal value in performing certain mechanistic assays. The ITN sample sharing policy will apply for the provision of samples to study or outside investigators (www.immunetolerance.org).

8. SAFETY MONITORING AND REPORTING

8.1 OVERVIEW

This section defines the types of safety data that will be collected under this protocol and outlines the procedures for appropriately collecting, grading, recording, and reporting those data. Adverse events that are classified as serious according to the definition of health authorities must be reported promptly (per Section 8.5, Reporting of Adverse Events and Serious Adverse Events/Events of Special Interest) to the sponsor (DAIT/NIAID). Appropriate notifications will also be made to the Immune Tolerance Network (ITN), site principal investigators, Institutional Review Boards (IRBs), and health authorities.

Information in this section complies with ICH Guideline E2A: Clinical Safety Data Management: Definitions and Standards for Expedited Reporting, ICH Guideline E-6: Guideline for Good Clinical Practice, 21CFR Parts 312 and 320, and applies the standards set forth in the National Cancer Institute (NCI), Common Terminology Criteria for Adverse Events (CTCAE), Version 5.0 (November 27, 2017): https://ctep.cancer.gov/protocoldevelopment/electronic_applications/docs/CTCAE_v5_Quick_Reference_8.5x11.pdf

8.2 **DEFINITIONS**

8.2.1 Adverse Event (AE)

Any untoward or unfavorable medical occurrence associated with the subject's participation in the research, whether or not considered related to the subject's participation in the research (modified from the definition of adverse events in the 1996 International Conference on Harmonization E-6 Guidelines for Good Clinical Practice) (from OHRP "Guidance on Reviewing and Reporting Unanticipated Problems Involving Risks to Subjects or Others and Adverse Events (1/15/07)" http://www.hhs.gov/ohrp/policy/advevntguid.html#Q2)

8.2.2 Adverse Reaction and Suspected Adverse Reaction (SAR)

Suspected adverse reaction (SAR) is any adverse event for which there is a reasonable possibility that the investigational drug caused the adverse event. For the purposes of safety reporting, 'reasonable possibility' means there is evidence to suggest a causal

relationship between the drug and the adverse event. A suspected adverse reaction implies a lesser degree of certainty about causality than adverse reaction, which means any adverse event caused by a drug (21 CFR 312.32(a) and ICH E2A).

An adverse reaction (AR) is any adverse event caused by the study drug. Adverse reactions are a subset of all suspected adverse reactions for which there is reason to conclude that the drug caused the event.

8.2.3 Unexpected Adverse Event/Reaction

A SAR is considered "expected" when it is listed in the investigator brochure, the package insert, or the protocol. A SAR is considered "unexpected" when its nature (specificity), severity, or rate of occurrence is not consistent with applicable product information as described in the safety information provided in the investigator brochure, the package insert, or the protocol (21 CFR 312.32(a) and ICH E2A). A serious unexpected suspected adverse reaction is referred to as a SUSAR. For this study, expectedness will be determined by product information provided in the investigator brochure, package insert, and protocol for brentuximab vedotin.

8.2.4 Serious Adverse Event (SAE)

An adverse event or suspected adverse reaction is considered "serious" if, in the view of either the investigator or Sponsor (DAIT/NIAID) it results in any of the following outcomes [21 CFR 312.32(a), and ICH E2A].

- 1. Death.
- 2. A life-threatening event: An AE or SAR is considered "life-threatening" if, in the view of either the investigator or Sponsor (DAIT/NIAID) its occurrence places the subject at immediate risk of death. It does not include an AE or SAR that, had it occurred in a more severe form, might have caused death.
- 3. Inpatient hospitalization or prolongation of existing hospitalization.
- 4. Persistent or significant incapacity or substantial disruption of the ability to conduct normal life functions.
- 5. Congenital anomaly or birth defect.
- 6. Important medical events that may not result in death, be life threatening, or require hospitalization may be considered serious when, based upon appropriate medical judgment, they may jeopardize the subject and may require medical or surgical intervention to prevent one of the outcomes listed above.

Elective hospitalizations are not to be reported as an SAE unless hospitalization is prolonged due to complications.

8.3 GRADING AND ATTRIBUTION OF ADVERSE EVENTS

8.3.1 Grading Criteria

The study site will grade the severity of adverse events experienced by the study subjects according to the criteria set forth in the National Cancer Institute's Common Terminology Criteria for Adverse Events (CTCAE) Version 5.0 (November 27, 2017), except for the grading of liver chemistry abnormalities, which is described in Section 8.3.2. This document (referred to herein as the NCI-CTCAE manual) provides a common language to describe levels of severity, to analyze and interpret data, and to articulate the clinical significance of all adverse events.

Adverse events will be graded on a scale from 1 to 5 according to the following standards in the NCI-CTCAE manual:

Grade 1 = mild adverse event.

Grade 2 = moderate adverse event.

Grade 3 = severe and undesirable adverse event.

Grade 4 = life-threatening or disabling adverse event.

Grade 5 = death.

For grading an abnormal value or result of a clinical or laboratory evaluation (including, but not limited to, a radiograph, an ultrasound, an electrocardiogram etc.), a treatment-emergent adverse event is defined as an increase in grade from baseline or from the last post-baseline value that doesn't meet grading criteria. Changes in grade from screening to baseline will also be recorded as adverse events if related to a study-mandated procedure, treatment, or change in treatment (but are not treatment-emergent). If a specific event or result from a given clinical or laboratory evaluation is not included in the NCI-CTCAE manual, then an abnormal result would be considered an adverse event if changes in therapy or monitoring are implemented as a result of the event/result.

For additional information and a printable version of the NCI-CTCAE manual, consult the NCI-CTCAE web site:

https://ctep.cancer.gov/protocoldevelopment/electronic_applications/docs/CTCAE_v5_Q uick_Reference_8.5x11.pdf

8.3.2 Grading of Liver Chemistry Abnormalities

For this study, AEs related to liver function testing will be graded relative to the upper limit of normal (ULN) as follows:

• Aspartate aminotransferase [AST] increased

o Grade 1: > ULN - 3.0x ULN

 \circ Grade 2: > 3.0x ULN - 5.0x ULN

- o Grade 3: > 5.0x ULN 20.0x ULN
- o Grade 4: > 20.0x ULN
- Alanine aminotransferase [ALT] increased
 - o Grade 1: > ULN 3.0x ULN
 - o Grade 2: > 3.0x ULN 5.0x ULN
 - o Grade 3: > 5.0x ULN 20.0x ULN
 - o Grade 4: > 20.0x ULN
- Alkaline phosphatase [ALP] increased
 - o Grade 1: > ULN -2.5x ULN
 - o Grade 2: > 2.5x ULN 5.0x ULN
 - o Grade 3: > 5.0x ULN 20.0x ULN
 - o Grade 4: > 20.0x ULN
- Blood bilirubin increased
 - o Grade 1: > ULN 1.5x ULN
 - o Grade 2: > 1.5x ULN 3.0x ULN
 - o Grade 3: > 3.0x ULN 10.0x ULN
 - o Grade 4: > 10.0x ULN

8.3.3 Attribution Definitions

The relationship, or attribution, of an adverse event to the study therapy regimen or study procedure(s) will initially be determined by the site investigator and recorded on the appropriate AE eCRF. Final determination of attribution for safety events that may be eligible for expedited reporting to the health authorities will be determined by the sponsor, DAIT/NIAID. The relationship of an adverse event to study therapy regimen or procedures will be determined using the descriptors and definitions provided in Table 1.

Table 1 Attribution of Adverse Events

Code	Descriptor	Relationship (to primary investigational product and/or other concurrent mandated study therapy o study procedure)				
UNRELATE	D CATEGORY					
1	Not related	The adverse event is clearly not related: there is insufficient evidence to suggest a causal relationship.				
RELATED (CATEGORIES					
2	Possible	The adverse event has a reasonable possibility to be related; there is evidence to suggest a causal relationship.				

3	Related	The adverse event is clearly related.

8.4 COLLECTING AND RECORDING ADVERSE EVENTS

8.4.1 Collection Period

All adverse events, regardless of NCI-CTCAE severity grade should be recorded in the study source documentation per the criteria below:

- Adverse events will be collected from the time the subjects signs the informed
 consent until he/she initiates study intervention or until he/she is determined to be
 ineligible to receive study intervention, if the investigator determines that the
 adverse event is related to a study-mandated procedure, treatment, or change in
 treatment.
- For all participants, adverse events will be collected from the time of initiation of study intervention until he/she completes study participation or until 30 days after he/she prematurely withdraws (without withdrawing consent) or is withdrawn from the study.

8.4.2 Collecting Adverse Events

Adverse events (including SAEs) may be discovered through any of these methods:

- Observing the subject.
- Interviewing the subject (e.g., using a checklist, structured questioning, diary, etc.).
- Receiving an unsolicited complaint from the subject.
- In addition, an abnormal value or result from a clinical or laboratory evaluation can also indicate an adverse event, as defined in Section 8.3.1.

8.4.3 Recording Adverse Events

Throughout the study, the investigator will record adverse events and serious adverse events as described previously (Section 8.2, Definitions) on the appropriate electronic CRF regardless of the relationship to study therapy regimen or study procedure. Events grade 2 or higher will be recorded on the appropriate AE case report form (eCRF) for this study. The only exception to the above is that Grade 1 or higher SARS-CoV-2 infection will be recorded.

Once recorded, an AE will be followed until it resolves with or without sequelae, or until the end of study participation, or until 30 days after the subject prematurely withdraws (without withdrawing consent)/or is withdrawn from the study, whichever occurs first.

An SAE will be followed until it resolves with or without sequelae OR until 30 days after the end of study participation.

If the AE is related to a laboratory or diagnostic evaluation, the evaluation that produced the value or result should be repeated until that value or result returns to normal or can be explained and the participant's safety is not at risk.

8.5 REPORTING ADVERSE EVENTS, SERIOUS ADVERSE EVENTS, AND EVENTS OF SPECIAL INTEREST TO SPONSOR: DAIT/NIAID

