1.4.1.1 Risk of Peripheral Neuropathy

Peripheral sensory neuropathy is the most commonly known risk of brentuximab vedotin, with peripheral motor neuropathy reported at a lower incidence. In the phase II pivotal clinical trial in HL, peripheral sensory neuropathy occurred in 42% of participants and peripheral motor neuropathy occurred in 11% of participants [56]. In this trial, brentuximab vedotin was administered every three weeks for a maximum of 16 doses. Peripheral neuropathy was the most common adverse event leading to treatment discontinuation or dose reduction. The majority of events were Grade 1 or Grade 2 peripheral sensory neuropathy events, consisting of numbness and tingling of fingers and toes. The median time to onset of any peripheral neuropathy event was 12.4 weeks, to Grade 2 events was 27.3 weeks, and to Grade 3 events was 38.0 weeks. The peripheral neuropathy events improved by at least one grade in 80% of those affected and resolved completely in 50% [56].

Similar results were reported in the phase II pivotal trial in ALCL and a phase III placebo-controlled trial of brentuximab vedotin for consolidation therapy after ASCT for HL [58, 60]. There were no Grade 4 peripheral neuropathy events in any of these three studies, however peripheral motor neuropathy events were categorized as serious in 4% of participants in the pivotal phase II HL trial [54]. Of note, in the pivotal phase II trials, 24% of participants had pre-existing peripheral neuropathy at baseline.

As described in the Investigator's Brochure (IB), the median duration of treatment was approximately 48 weeks in the phase III trial of consolidation therapy following ASCT in HL patients [60]. Worsening of neuropathy was mitigated by reduction and delay in dosing. Peripheral neuropathy events tended to worsen with longer treatment exposure, with the first onset at approximately 12 weeks after the first dose of brentuximab vedotin. Grade 3 peripheral neuropathy events occurred at a median of approximately 34 weeks. The majority of events improved or resolved by a median of approximately 23 weeks.

Patients enrolled in a retreatment or extension treatment trial had more peripheral neuropathy at baseline compared to the pivotal phase II studies, and also developed more peripheral neuropathy events [65].

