As of August 2020, a search of the clinical trial database found treatment emergent peripheral neuropathy (sensory and motor) occurred in 1394 participants (55%). Most of the events (1177, or 47%) were \leq Grade 2 [65].

The prescribing information for brentuximab vedotin as monotherapy reports 62% of patients experienced any grade of neuropathy. The median time to onset was three months (range 0-12). Of patients experiencing neuropathy, 62% had complete resolution of symptoms, 24% had partial improvement, and 14% had no improvement at the time of the last evaluation. The prescribing information recommends temporary discontinuation and subsequent dose modification for Grade 2 or Grade 3 peripheral neuropathy, and permanent discontinuation for Grade 4 peripheral neuropathy [55]. In the trial described in this protocol, the dose of brentuximab vedotin will be suspended if a participant

develops Grade 2 peripheral neuropathy and restarted at a lower dose if the peripheral neuropathy resolves. Brentuximab vedotin will be permanently discontinued for Grade 3 or greater peripheral neuropathy (see section 5.2). Participants will be excluded if they are older than 70 years of age, if they have diabetes, or if they have pre-existing peripheral neuropathy (see section 4.2). In addition, participants will be monitored for peripheral neuropathy throughout the trial.

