8.11.2 Protocol-Defined Interim Safety Reviews

Interim safety reviews will be undertaken by a Safety Review Committee (SRC) comprised of a subgroup of the DSMB. The study design (section 3.1) specifies interim safety analysis and review by the SRC after each of the first two dosing cohorts have completed 12 weeks of therapy. Approval by the SRC is required following review of the 12-week interim safety data prior to proceeding to the next higher dosing cohort.

Interim safety analysis will also be conducted after each of the first two dosing cohorts have completed 24 weeks of therapy.

Following each protocol-specified interim safety review, the SRC can recommend actions regarding study conduct, including, but not limited to, the following:

- 1. Continue the study as planned.
- 2. Add participants to an existing dosing cohort.
- 3. Reduce the number of weeks of study drug administration for the next higher dosing cohort.
- 4. Stop the study.

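### Grade 1 peripheral neuropathy stays off the AE eCRF and the interim package does not name the neuropathy assessment, so the SRC is not assured of seeing early neuropathy when it decides on escalation at week 12

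*Protocol*

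**What the plan says.** **Recording.** Section 8.4.3 of the protocol states: "Events grade 2 or higher will be recorded on the appropriate AE case report form (eCRF) for this study". It adds: "The only exception to the above is that Grade 1 or higher SARS-CoV-2 infection will be recorded". Section 8.5.1 uses the same Grade 2 threshold for timely reporting. Lower grades are kept at the site, under Section 8.4.1: "All adverse events, regardless of NCI-CTCAE severity grade should be recorded in the study source documentation per the criteria below".

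**Named neuropathy measures.** Secondary endpoint 3 (Section 3.4.2) starts at Grade 2. The event of special interest (Section 8.5.2) and stopping rule 5 (Section 8.11.3) start at Grade 3. The secondary objective on neuropathy (Section 2.2) has no grade limit.

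**Assessment.** Section 6.3 describes a structured neuropathy assessment covering pin and vibration sensibility, strength, and motor, sensory and autonomic symptoms. Appendix 1 schedules it at screening and at weeks 3, 6, 9 and 12, among other visits. Section 11 has visit data entered on the relevant eCRFs.

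**Escalation.** Section 8.11.2 states: "Approval by the SRC is required following review of the 12-week interim safety data". This applies after cohorts 1 and 2. Section 9.2.7 takes the interim content from Section 9.2.6. That section gives an open list which names AEs and physical examination results but not the neuropathy assessment.

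**Expected timing.** Section 1.4.1.1 reports, from the pivotal Hodgkin lymphoma trial: "The median time to onset of any peripheral neuropathy event was 12.4 weeks, to Grade 2 events was 27.3 weeks". The Grade 3 median is 38.0 weeks.

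**Week 28.** Under notes 4 and 5 of Appendix 1, this visit is remote and has no neuropathy assessment unless the participant is under follow-up for a neuropathy AE.

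**The concern.** Section 1.4.1.1 presents sensory neuropathy as the best-known risk of the drug and says that events tended to worsen with longer exposure. Grade 1 neuropathy is therefore the early form of the toxicity of most interest. Week 12 is when the SRC must approve the next dose. It falls close to the median onset of any neuropathy and well before the median onset of Grade 2. AE listings cut at Grade 2 would leave out the part of the signal most likely to be present, and no other named item in the interim package is certain to supply it.

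The same rule may also affect follow-up. Section 8.4.3 ties follow-up of an AE to its having been recorded. On a plain reading, a participant with only Grade 1 neuropathy has no AE entry under follow-up and so would not have the week-28 assessment. The next scheduled examination after week 24 is then week 36, and the 27.3-week Grade 2 median lies between the two.

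**Working it through.** **Check of the plan's own figures.** Table 2 (Section 9.3) uses 1 − (1 − p)^n. For n = 6 and p = 0.1, 0.2, 0.3 this gives 0.469, 0.738 and 0.882. For n = 3 it gives 0.271, 0.488 and 0.657. All six cells reproduce. The protocol gives no figure for neuropathy visible at week 12, so the same formula is applied to its onset data.

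**Inputs from the protocol.**
- Median onset: 12.4 weeks for any grade, 27.3 weeks for Grade 2 (Section 1.4.1.1; 1.8 mg/kg every three weeks, Section 1.3.2.1).
- Any-grade incidence: 55% in the clinical trial database and 62% in the prescribing information (Section 1.4.1.1). The pivotal Hodgkin trial reports 42% for sensory neuropathy alone.
- Active participants per cohort: 6 (Section 9.3).

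**Assumptions.**
- Onset is exponential (k = 1 below), with other shapes as a check.
- The protocol gives no split between Grade 1 and Grade 2. The share s of cases that ever reach Grade 2 or higher is taken as 30% to 70%. A floor of about 16% follows from the database counts, as the share above Grade 2: (1394 − 1177)/1394 = 0.156.

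**Step 1. Share of eventual onsets that fall by week 12**, F = 1 − 0.5^((12/median)^k), with k = 1:
- any grade: 1 − 0.5^(12/12.4) = 0.489
- Grade 2: 1 − 0.5^(12/27.3) = 0.263

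**Step 2. Any-grade neuropathy by week 12.**
- 55%: 0.55 × 0.489 = 0.269 per participant, and 1 − (1 − 0.269)^6 = 0.847
- 62%: 0.62 × 0.489 = 0.303 per participant, and 1 − (1 − 0.303)^6 = 0.885
- 42%: 0.42 × 0.489 = 0.205 per participant, and the chance is 0.75

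**Step 3. Grade 2 or higher by week 12**, at 55% incidence.
- s = 0.30: 0.55 × 0.30 × 0.263 = 0.043, and 1 − (1 − 0.043)^6 = 0.23
- s = 0.70: 0.55 × 0.70 × 0.263 = 0.101, and 1 − (1 − 0.101)^6 = 0.47

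At 62% incidence the same range of s gives 0.26 to 0.52.

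**Step 4. Share of week-12 neuropathy that is Grade 1 only**, 1 − s × F(Grade 2)/F(any). Incidence cancels, so this step does not depend on the 55% or 62%.

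| Onset shape k | s = 0.30 | s = 0.70 | s above which Grade 1 is no longer the majority |
|---|---|---|---|
| 0.7 | 0.80 | 0.54 | 0.76 |
| 1 | 0.84 | 0.62 | 0.93 |
| 1.5 | 0.89 | 0.74 | none |
| 2 | 0.92 | 0.82 | none |

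Grade 1 is the majority throughout the range considered. This is an inference from the stated medians, not a figure in the protocol.

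**The case against.** Four objections carry weight.

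**The data have another route.** A reader might infer that the SRC cannot see Grade 1 neuropathy at all. The protocol does not support that. The threshold applies to the AE form only. The structured assessment at weeks 3 to 12 is visit data for the eCRF, and the Section 9.2.6 list is open and names physical examination results. Interim displays are also commonly specified in the SAP, which is not at hand. This stands, and it limits the point to a lack of assurance. It does not remove the point, because the list is permissive, does not name the assessment, and Section 6.3 attaches no CTCAE grade to the signs and symptoms collected.

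**The figures come from other patients and a higher dose.** The onset medians are for lymphoma patients at 1.8 mg/kg. In the pivotal phase II trials 24% had neuropathy at baseline, whereas this trial excludes neuropathy and diabetes. The SRC's approvals follow the 0.6 and 1.2 mg/kg cohorts, and no escalation follows 1.8 mg/kg. This also stands. The probabilities are an upper-end illustration, not estimates for either decision. The calculation also pairs incidence and onset from different sources.

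**The threshold is coherent.** Grade 2 matches secondary endpoint 3, the suspension trigger in Section 5.2.3 and the reporting rule in Section 8.5.1. There is no internal contradiction. The protocol also states no escalation criterion that Grade 1 neuropathy would trigger, so it cannot be said that the rule would lead to a wrong escalation.

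**Other safeguards exist.** The week-24 SRC reviews, stopping rule 5 and ad hoc DSMB review all remain, and Grade 1 events are in source documents. None of these places Grade 1 neuropathy before the SRC at week 12.

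**Conclusion.** The point holds as a gap in assurance. Grade 1 neuropathy is off the AE eCRF, no exception is made for it, and the interim package does not name the assessment that would show it. The protocol's onset medians make it likely that most neuropathy arising by week 12 would be Grade 1: 62% to 84% under exponential onset if 30% to 70% of cases ever reach Grade 2. In a group of 6 at 55% any-grade incidence, the chance of at least one case is about 0.85 for any grade and 0.23 to 0.47 for Grade 2 or higher.

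The result rests on the onset shape, the assumed grade split, and the carry-over of timing from lymphoma patients at 1.8 mg/kg. Absolute rates at 0.6 and 1.2 mg/kg are unknown and probably lower. The week-28 consequence depends on reading follow-up as applying only to recorded AEs.

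A reader might go further and infer that the rule hides a neurotoxic dose or is an error in the plan. The documents support neither. It is a design choice that can be improved cheaply for the main known toxicity.

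**What to change.** 1. In Section 8.4.3, extend the existing exception so that Grade 1 or higher peripheral neuropathy is recorded on the AE eCRF alongside Grade 1 or higher SARS-CoV-2 infection. Align Section 8.5.1.
2. In Sections 9.2.6 and 9.2.7, name any-grade peripheral neuropathy and the neuropathy assessment results, listed by participant, as part of each interim safety package.

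The cost is a few more eCRF entries per participant, from examinations already scheduled, and a minor protocol amendment with the approvals in Section 12.1. No endpoint or dose rule changes, and the visit schedule stays as it is. One consequence should be accepted knowingly: under the existing Appendix 1 notes, a participant with an open Grade 1 neuropathy entry would qualify for the week-28 assessment, and that visit would then not be remote.
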